8.7.4 Vital signs

Descriptive statistics for actual measurements of vital signs (systolic/diastolic blood pressure (mmHg), respiratory rate (breaths/min), heart rate (beat/min), temperature (°C)), weight (kg) and BMI (kg/m²), and changes from baseline for each time point will be presented by cohort.

Listing of vital signs data will be presented.

8.7.5 Physical examinations

A listing will be provided for physical examination by cohort, subject, visit, body system, and description of abnormalities.

Final Analysis Statistical Analysis Plan (SAP)

8.7.6 Electrocardiograms

Shift tables from baseline (Normal/Abnormal-clinically significant/Abnormal–not clinically significant) to each time point and to worst post-baseline ECG interpretation will be summarized for ECG interpretation data. Descriptive statistics for actual and changes from baseline will be displayed for heart rate (msec), QRS interval (msec), RR interval (msec), PR interval (msec), QT interval (msec), QTc interval (msec).

ECG data will be listed overall and a separate listing for any clinically significant finding in ECG values will be provided.

8.7.7 ECOG performance status

Shift table for performance status (0 to 5 grades) of subjects from baseline to the worst post-baseline visit will be presented by cohort.

A listing of the performance status of subjects will be provided by visit.

8.8 Other analysis

8.8.1 Statistical analysis for PK data

AFM13 serum concentrations will be summarized by cohort, study cycle, and nominal time points. All table summaries and figures for PK concentrations will be compiled using the PK set and will be presented by cohort. For concentration values below the limit of quantification (BLQ), a concentration value of zero will be included for the computation of arithmetic mean and a concentration value of $\frac{1}{2}$ LLOQ will be included for the computation of geometric mean.

Individual subject listings for concentration data will be provided. Plots of serum concentrations (geometric mean (+/- coefficient of variation (CV)) will be presented in both original and semi-logarithmic scales.

PK parameters data will be converted into Study Data Tabulation Model (SDTM) datasets and will be summarized in a separate noncompartmental analysis (NCA) report.

Final Analysis Statistical Analysis Plan (SAP)

8.8.3 Quality of life analyses

EQ-5D

EQ-5D will be used to assess the subject’s 5 dimensions - mobility, self-care, usual activities, pain/discomfort and anxiety/depression. Shift tables for EQ-5D pain/discomfort score (“no pain or discomfort”, “moderate pain or discomfort” and “extreme pain and discomfort”) from baseline to each visit will be presented for cohorts A and B by visit using FAS. The health state scale actual and change from baseline values will be also summarized.

Skindex-29

The Skindex-29 is composed of 29 items investigating the three domains: Emotions, Symptoms and Functioning. These domains will be derived for each visit as below:

Domains and clusters:

Domains/ Scale	Number of items	Clusters of items	Direction of domains
Emotions	10	3; 6; 9; 12; 13; 15; 21; 23; 26; 28	Higher score = higher impact of skin disease
Symptoms	7	1; 7; 10; 16; 19; 24; 27	
Functioning	12	2; 4; 5; 8; 11; 14; 17; 20; 22; 25; 29; 30	

Scoring procedure of each domain:

1. All responses are transformed to a linear scale of 100.
 - Never = 0
 - Rarely = 25
 - Sometimes = 50
 - Often = 75
 - All the time = 100

2. A scale score is the mean of non-missing items in a given scale (note: item 18 is a single item, not included in scoring):
 - a. If responses to more than 25% of items are missing overall the questionnaire is eliminated (ie, if > 7 items are missing among the 29 items).
 - b. If any scale has more than 25% of the responses missing, the scale is missing (ie, if > 2 items for Emotions or > 1 item for Symptoms or > 3 items for Functioning are missing).

Final Analysis Statistical Analysis Plan (SAP)

- c. An item with multiple answers is considered missing.

Sum score:

The sum score is derived as the average of the three scale scores for each subject and visit.

The summary statistics of absolute and change from baseline values for the 3 scale scores and the sum score will be provided at each visit for cohort C using FAS.

Supportive by-subject listings will also be provided for EQ-5D-3L and Skindex-29.

8.8.4 Biomarker analysis

[REDACTED]

8.8.5 Subgroup analysis

The following subgroup analyses will be performed for the final analysis:

- [REDACTED]
- [REDACTED]
- [REDACTED]
- [REDACTED]
- [REDACTED]
- [REDACTED]
- [REDACTED]
- [REDACTED]
- [REDACTED]
- [REDACTED]
- [REDACTED]
- [REDACTED]
- [REDACTED]
- [REDACTED]
- [REDACTED]
- [REDACTED]
- [REDACTED]
- [REDACTED]
- [REDACTED]
- [REDACTED]

Final Analysis Statistical Analysis Plan (SAP)

- [REDACTED]

[REDACTED]

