5.4.9 Disease Assessment

Imaging assessments, including FDG-PET and CT assessments for Cohorts A and B (PTCL) and CT scan or MRI for Cohort C (TMF), will be performed at Screening and every 8 weeks for the first 3 assessments, then every 12 weeks thereafter, as well as at the time of suspected clinical progression, as described in Schedule of Assessments [REDACTED]. This scheduling is regardless of any treatment/cycle delays that may occur. All imaging assessments will be

conducted according to local institutional practice and the same modality should be used for initial staging at Screening and all restaging assessments.

[REDACTED]

[REDACTED]

[REDACTED]

[REDACTED]

Further details of the conduct and processing of imaging assessments will be described in the Imaging Manual for the study.

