6.7 Duration of Treatment

Treatment with AFM13 should continue until disease progression, unacceptable toxicity, Investigator discretion or withdrawal of consent.

[REDACTED]

[REDACTED]

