8.5 Exposure to study treatment

8.5.1 AFM13 study drug

The following parameters, relative to AFM13 drug administration, will be calculated and summarized by cohort using descriptive statistics for the FAS:

- Number of infusions of AFM13.
- Dose exposure (weeks).
- Cumulative dose (mg).
- Dose intensity (mg/week).
- Relative dose intensity (%).

Final Analysis Statistical Analysis Plan (SAP)

The number of infusions with interruptions and dose modifications (including the reasons) will be also summarized by cohort. The number of subjects who take the 200 mg dose during the entire study will be also summarized (see Section 8.8.5).

Listing will be provided for AFM13 administration and exposure.

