As the study design is based on a Simon's two stage design (See Section 5), an exact binomial test will be performed to analysed the ORR of the Cohorts A and C at the final analysis only. The one-sided p-value will be displayed. The tested hypotheses are as follows for each cohort:

Cohort A: $H_0: p \leq 0.25$

$H_1: p > 0.25$

Cohort C: $H_0: p \leq 0.05$

$H_1: p > 0.05$

For all response assessments, swimmer plots will be presented. All response assessments will be also listed.

The above analyses (overall response, BOR and ORR) will be performed for each cohort and for:

Response evaluator	Population of analysis	Analysis order
IRC	FAS	Primary analysis
IRC	FAS with at least one post-baseline efficacy assessment	Sensitivity analysis, if deemed necessary (based on the number of subjects included in that population after the Classification Meeting)
IRC	COVID analysis set	Sensitivity analysis, if deemed necessary (based on the number of subjects included in that population after the Classification Meeting)
IRC	PP set	Sensitivity analysis, if deemed necessary (based on the number of subjects included in that population after the Classification Meeting)
Investigator	FAS	Secondary analysis
██████████	████████████████████	██ ██ ██

These analyses will be also repeated for the subgroups defined in Section 8.8.5 for the FAS.

Duration of response (DOR)

The DOR is defined as time from first assessment of PR or CR to the first assessment of progressive disease or death due to any cause separately for IRC and Investigator using respectively only IRC or Investigator assessments. DOR will be censored for IRC assessments using Table 1 and Investigator assessments using Table 3 when analyses are performed on FAS or PP set. The Table 2 and Table 4 will be used when the analyses are performed on the COVID analysis set:

Final Analysis Statistical Analysis Plan (SAP)

Table 1: Independent Review Committee Assessments (IRC) Censoring Rules

Event	Event or censored date	Event or censored
Progression (as determined by IRC)	Date of progression (as determined by IRC)	Event
Death due to any cause	Date of death	Event
PD (as determined by IRC) or death after 1 missed assessment (ie, ≥ 59 days between 2 assessments until Cycle 4 and ≥ 87 days from Cycle 5)	Date of PD (as determined by IRC) or death	Event

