Final Analysis Statistical Analysis Plan (SAP)

[REDACTED]	[REDACTED]	[REDACTED]
[REDACTED]	[REDACTED]	[REDACTED]
[REDACTED]	[REDACTED]	[REDACTED]

Note: Only disease assessments collected in the CRF are included in the analysis.

* The new anti-cancer therapy information is only collected on the “Survival follow-up’ page but no date is collected. Consequently, it is assumed that the new therapy starts between the follow-up where the question “Did the patient start any new anti-cancer therapies?” is “Yes” and the previous follow-up. The subject will be censored at the last disease assessment prior or on this previous visit.

DOR will be summarized and listed by cohort and for CT and FDG-PET (=PET-CT) based responses separately. Duration of CR and duration of PR will be also reported separately.

DOR will be analyzed using Kaplan-Meier median, its 95% CI (and 25th and 75th percentile) and the estimates at 3, 6, 9, 12, etc months.

Theses analyses will be also repeated for the subgroups defined in Section 8.8.5 for the FAS.

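### If the 'entire study' 200 mg group is one of the SAP 8.8.5 subgroups, its ORR and DOR are confounded with time on treatment

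*SAP*

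**What the plan says.** Four parts of the plan bear on this.

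- **The group.** SAP 8.5.1, on exposure, states: "The number of subjects who take the 200 mg dose during the entire study will be also summarized (see Section 8.8.5". The section it points to is headed as the subgroup analysis and opens with "The following subgroup analyses will be performed for the final analysis". The list that follows is redacted.
- **Its use for efficacy.** SAP 8.6.2 says, after overall response, BOR and ORR: "These analyses will be also repeated for the subgroups defined in Section 8.8.5 for the FAS". After DOR it says the same: "Theses analyses will be also repeated for the subgroups defined in Section 8.8.5 for the FAS". Neither sentence makes an exception for any subgroup.
- **Doses can change.** SAP 8.5.1 also states: "The number of infusions with interruptions and dose modifications (including the reasons) will be also summarized by cohort".
- **Time on treatment depends on outcome.** Protocol 6.7 states: "Treatment with AFM13 should continue until disease progression, unacceptable toxicity, Investigator discretion or withdrawal of consent". Under Protocol 5.4.9, imaging "will be performed at Screening and every 8 weeks for the first 3 assessments, then every 12 weeks thereafter". With weekly dosing, about 8 infusions therefore precede the first response assessment. SAP 8.6.2 counts subjects without a post-baseline response assessment as non-responders.

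**The concern.** Whether a subject took 200 mg throughout is known only after the last infusion. A subject who progresses at the first scan has had few infusions at which the dose could change, and so tends to remain in the full-dose group by default. A responder treated for months must pass many more infusions unchanged to stay in it. Membership is then partly a consequence of response, which is a form of immortal-time bias.

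DOR has the same problem. Among responders, those with longer responses are treated longer and have more chances to leave the group.

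A table of ORR and DOR for this group would naturally be read as activity at the full dose. It could show a difference between full-dose and modified-dose subjects when dose has no effect at all.

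**Working it through.** The documents give no figure for this subgroup and no rate or timing of dose changes, so there is nothing to reproduce. All rates below are assumptions. In every case the true ORR is the same whatever the dose.

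**1. Constant chance of a change per infusion.** Assume ORR 0.33, 8 infusions for non-responders (progression at about the first scan), 24 for responders, and a chance p per infusion of a dose other than 200 mg.

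P(always 200 mg) = (1−p)^n

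ORR in the full-dose group = 0.33(1−p)^24 / [0.33(1−p)^24 + 0.67(1−p)^8]

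At p = 0.01: 0.99^24 = 0.786 and 0.99^8 = 0.923. The full-dose share is 0.33×0.786 + 0.67×0.923 = 0.259 + 0.618 = 0.877. ORR in the group is 0.259/0.877 = 0.295. In the remainder it is (0.33−0.259)/(1−0.877), which is 0.577 before rounding.

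| p per infusion | Responder infusions | Share in full-dose group | ORR, full dose | ORR, others |
|---|---|---|---|---|
| 0.01 | 24 | 0.88 | 0.295 | 0.577 |
| 0.03 | 24 | 0.68 | 0.232 | 0.542 |
| 0.05 | 24 | 0.54 | 0.178 | 0.509 |
| 0.03 | 16 | 0.73 | 0.279 | 0.468 |

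**2. A different model of treatment time.** Let time on treatment be exponential with mean t weeks, with a weekly hazard h of a first dose change. Then P(always 200 mg) = (1/t)/(1/t + h) = 1/(1 + ht). Use ORR 0.25 (the Cohort A null value in SAP 8.6.2, as an anchor only), with t = 8 for non-responders and 24 for responders.

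At h = 0.01 the two probabilities are 1/1.08 = 0.926 and 1/1.24 = 0.806. Full-dose ORR = 0.25×0.806/(0.25×0.806 + 0.75×0.926) = 0.225, against 0.466 in the others. At h = 0.02 the pair is 0.207 and 0.439. At h = 0.05 it is 0.175 and 0.389.

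**3. Test of the sign.**

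- *Equal time on treatment* (mean 8 weeks for both): the retention probabilities cancel, giving 0.250 against 0.250.
- *Early changes, equally likely in both groups* (probability 0.15 each): again 0.250 against 0.250.
- *Early changes concentrated in subjects who then fail* (probability 0.25 in non-responders, 0.10 in responders): full-dose ORR = 0.25×0.90/(0.25×0.90 + 0.75×0.75) = 0.225/0.7875 = 0.286. In the others it is 0.025/(0.025 + 0.1875) = 0.118. The bias reverses.

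**4. DOR.** Under model 1 at p = 0.03, a responder with 16 infusions stays in the full-dose group with probability 0.97^16 = 0.61, and one with 24 infusions with probability 0.97^24 = 0.48. Longer responders are removed preferentially. This also rests on changes accruing with time.

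**The case against.** The strongest reply is that the key text cannot be read. The visible part of SAP 8.8.5 does not show how the group is defined, what it is compared with, whether ORR or DOR is reported for it, or whether a landmark applies. The pointer sits under an exposure count, which is a legitimate use. A split by assigned or starting dose cannot be fully excluded, since Protocol 8 allows summaries by dose where that differs from cohort.

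This stands as a limit on certainty. The redaction is not a defect, and a reader should not infer from it that a safeguard is absent. The natural reading nevertheless remains a post-baseline group. The words in SAP 8.5.1 cover the whole study, which fits poorly with a dose fixed at entry or at a landmark, and the reference is to the section whose subgroups SAP 8.6.2 carries into the efficacy analyses.

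A second reply is that direction and size are uncertain. This also stands. A reader might infer that full-dose ORR must be biased low, but step 3 shows that the bias can be nil or reversed. At 1% per infusion the full-dose ORR moves only from 33% to about 30%. The 58% belongs to the remaining 12% of subjects, and the documents do not show that such a comparator will be reported.

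A reader might also count the every-other-week option in SAP 3.3 as leaving the group. Because that option requires a response, it would strengthen the low bias. The visible text describes a change of schedule and does not say that it changes the 200 mg dose.

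**Conclusion.** The point holds conditionally. If the group in SAP 8.5.1 is one of the SAP 8.8.5 efficacy subgroups, its ORR and DOR are confounded with time on treatment and cannot be read as a dose effect. Full-dose ORR is probably biased low if dose changes accrue with time on treatment. Under the assumed inputs in models 1 and 2, the spurious gap between full-dose and other subjects is about 19 to 33 percentage points (0.468 − 0.279 to 0.509 − 0.178), with no true dose effect. The sign is not established, because the documents give neither the rate nor the timing of dose changes.

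A reader might infer that the main result is compromised. It is not. The primary ORR is computed on all treated subjects in the FAS and does not use this grouping. No visible text bases a decision on the subgroup.

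**What to change.** Keep the whole-study 200 mg group in SAP 8.5.1 as a descriptive exposure count only. If response by dose is reported, state the following in SAP 8.8.5:

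- **ORR:** define the group by doses actually given up to the first post-baseline disease assessment (Week 8 landmark). Do not require that all planned infusions were received, because that would select on tolerability and drop subjects with innocent delays.
- **Subjects off treatment before the landmark:** show them in a separate row, still counted as non-responders in line with the SAP 8.6.2 rule for subjects without a post-baseline assessment, so that the whole FAS is accounted for.
- **DOR:** define the group by doses given up to first response.
- **Both:** later changes do not alter membership, and the table is labelled descriptive. A landmark removes the dependence on later treatment time, but not differences between subjects whose dose changed early and those whose dose did not.

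The cost is SAP wording, one re-derived flag and a slightly more complex subgroup table. If the redacted text already does this, the sponsor need only confirm it and align the wording of SAP 8.5.1.

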8.9 Interim analysis

[REDACTED]

[REDACTED]

[REDACTED]

[REDACTED]

[REDACTED]

[REDACTED]

[REDACTED]

The following analyses will be generated for the interim analysis:

- Disposition.
- Demographic and baseline characteristics.
- Disease characteristics.
- Exposure to treatment (AFM13 and premedications)
- Overall response.
- Duration of response.
- Adverse events.

**Final Analysis
Statistical Analysis Plan (SAP)**

9

[REDACTED]

[REDACTED]

[REDACTED]

[REDACTED]

[REDACTED]

[REDACTED]

[REDACTED]

Final Analysis Statistical Analysis Plan (SAP)

11 APPENDIX A

For each disease assessment visit, the visit name will be derived as follows:

Step 1: Determine the minimum and maximum dates per visit as follows:

For Lugano (within the same disease assessment visit):

DateINF = MIN (

TU.TUDTC (Imaging (modified Lugano)),
TR.TRDTC (Imaging (modified Lugano)),
TU.TUDTC (New Lesions (modified Lugano)),
TR.TRDTC (New Lesions (modified Lugano)),
TU.TUDTC (Tissue Sites Involved),
TR.TRDTC (Tissue Sites Involved),
TU.TUDTC (FDG-PET),
TR.TRDTC (FDG-PET),
PR.PRDTC (FDG-PET))

DateSUP = MAX (

TU.TUDTC (Imaging (modified Lugano)),
TR.TRDTC (Imaging (modified Lugano)),
TU.TUDTC (New Lesions (modified Lugano)),
TR.TRDTC (New Lesions (modified Lugano)),
TU.TUDTC (Tissue Sites Involved),
TR.TRDTC (Tissue Sites Involved),
TU.TUDTC (FDG-PET),
TR.TRDTC (FDG-PET),
PR.PRDTC (FDG-PET))

Final Analysis Statistical Analysis Plan (SAP)

For Olsen (within the same disease assessment visit):

DateINF = MIN (
TU.TUDTC [Imaging (Olsen)],
TR.TRDTC [Imaging (Olsen)],
TU.TUDTC (New Lesions (Olsen)),
TR.TRDTC (New Lesions (Olsen)),
FA.FADTC (TNMB Staging),
QS.QSDTC (mSWAT),
QS.QSDTC (CAILS),
LB.LBDTC (Flow cytometry for Olsen criteria),
PR.PRSTDTC (Lesion Photography),
PR.PRSTDTC (Biospy (Olsen criteria)),
MI.MIDTC (Biospy (Olsen criteria))

DateSUP = MAX (
TU.TUDTC [Imaging (Olsen)],
TR.TRDTC [Imaging (Olsen)],
TU.TUDTC (New Lesions (Olsen)),
TR.TRDTC (New Lesions (Olsen)),
FA.FADTC (TNMB Staging),
QS.QSDTC (mSWAT),
QS.QSDTC (CAILS),
LB.LBDTC (Flow cytometry for Olsen criteria),
PR.PRSTDTC (Lesion Photography),
PR.PRSTDTC (Biospy (Olsen criteria)),
MI.MIDTC (Biospy (Olsen criteria))

Final Analysis Statistical Analysis Plan (SAP)

Step 2: Assign the visit name as follows:

If $(SV.SVSTDTC - 7 \leq DateINF \leq SV.SVSTDTC + 7)$

or $(SV.SVSTDTC - 7 \leq DateSUP \leq SV.SVSTDTC + 7)$

or $(DateINF < SV.SVSTDTC - 7 \text{ AND } DateSUP > SV.SVSTDTC + 7)$ then AVISIT = SV.VISIT;

Else AVISIT = "Unscheduled".

Notes:

- Visits planned per protocol to have disease assessments are considered from SV.
- If at least one assessment of the disease assessment visit is within the time-window then all the assessments are assigned to the visit.

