5.4.10 Response Assessment

Response assessment will be performed in conjunction with the post dose disease assessments ie, every 8 weeks for the first 3 assessments, then every 12 weeks thereafter, as well as at the time of suspected clinical progression, as described in Schedule of Assessments [REDACTED]

Response assessment will follow the modified Lugano Classification Revised Staging System for malignant lymphoma ([Cheson, 2014](#)) for subjects with PTCL (Cohorts A and B) and the Olsen Criteria ([Olsen, 2011](#)) for subjects with TMF (Cohort C) [REDACTED]

The modified Lugano Classification refers to the protocol's separate use of PET-CT based response criteria from CT-based response criteria from the Lugano Classification to guide clinical decisions and assessment of overall response. The CT-based overall response will be one of the secondary endpoints.

For Cohort C (TMF), the Olsen Criteria determines the global response (GR) based on the following:

- skin assessment by the modified Severity Weighted Assessment Tool (mSWAT) and Composite Assessment of Index Lesions Severity (CAILS)

- lymph node assessment by CT (or MRI)
- visceral disease assessment by CT (or MRI)
- blood assessment by flow cytometry (ie, CD4-positive/CD7-negative and CD4-positive/CD26-negative subsets)

[REDACTED]

Assessments will be performed both locally and centrally, and all imaging scans (PET-CT for Cohorts A and B, CT or MRI for Cohort C) will be collected for independent review. Treatment decisions should be based on the local disease assessment.

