6.8 AFM13 Dose Delays or Interruptions

The dosing schedule for Study visits that include AFM13 administration permit a tolerance window of ± 1 day at Cycle 1 Day 8, then a ± 3 -day tolerance window for all visits thereafter. However, the minimum time period between any two consecutive AFM13 administrations cannot be less than 3 days.

AFM13 dosing delays may be permitted in the case of medical/surgical events or logistical reasons not related to study therapy (eg, elective surgery, unrelated medical events, subject vacation and/or holidays) after obtaining approval from the Sponsor.

[REDACTED]

[figure not shown]
[REDACTED]

[figure not shown]
[REDACTED]

[REDACTED]

[REDACTED]

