8 STATISTICAL METHODS

8.1 General statistical conventions

All statistical procedures will be completed using SAS version 9.4 or higher.

Unless otherwise stated, all statistical testing will be two-sided and will be performed using a significance (alpha) level of 0.05. Two sided 95% confidence intervals (CI) will be provided when relevant.

Continuous variables will be summarized using descriptive statistics, including number of subjects (n), mean, median, standard deviation (SD), minimum (Min) and maximum (Max).

For categorical variables, summaries will include counts of subjects and percentages. Percentages will be rounded to one decimal place.

For summary purposes, baseline will be defined as the last available pre-dose value.

[REDACTED]

All subject data, including those derived, will be presented in individual subject data listings. Unless otherwise stated, unscheduled visit results will be included in date/time chronological order, within subject listings only. All listings will be sorted by cohort, subject number, assessment date/time and visit. Patient's sex and age will be also stated on each listing. Unless otherwise stated, data listings will be based on FAS.

Subjects who were screened and have signed the informed consent form (ICF) but did not receive any treatment will be listed including reason for screen failure or not being treated and any SAE (this will be recorded in the medical history). These subjects will not be part of any summary table except for summarizing disposition.

Final Analysis Statistical Analysis Plan (SAP)

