8.6.1.4 Derivation of post-baseline disease assessments visits

In the CRF, the post-baseline disease assessments are not linked to study visits. Consequently, this will be performed by programming as per APPENDIX A.

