8.6.2 Analysis of efficacy endpoints

The primary endpoint is based on the IRC PET-CT-based metabolic responses. Secondary endpoints are based

Final Analysis Statistical Analysis Plan (SAP)

on IRC CT based radiologic responses and on Investigator (CT or FDG-PET (=PET-CT)) responses.

Overall response

Within each visit an overall response will be determined by the IRC and Investigator on CT-based radiographic responses and FDG-PET (=PET-CT) based metabolic responses separately utilizing the modified Lugano Classification revised staging system for malignant lymphoma (Cheson 2014) for Cohorts A and B (PTCL) and the Olsen Criteria (Olsen 2011) for Cohort C (TMF).

Subjects who cannot be evaluated for response will be categorized as not evaluable (NE).

Best overall response (BOR)

The best overall response is the best response recorded from the start of the treatment until disease progression/recurrence or death. All disease responses obtained after progressive disease, start of new anti-cancer therapy or a transplant are excluded from the best overall response. Best is defined as the first response when all a subject's response assessments are sorted by complete response/complete radiologic response/complete metabolic response (CR), partial response/partial remission/partial metabolic response (PR), stable disease/no metabolic response (SD), pseudoprogression, progressive disease/progressive metabolic disease (PD), not evaluable (NE).

The subject's best response assignment will depend on the achievement of the measurement criteria (confirmation is not required). BOR will be summarized using a frequency table by cohort. For Cohorts A and B, BOR is derived for radiographic (using only CT-based responses) and metabolic responses (using only FDG-PET (=PET-CT) based responses) separately.

Overall response rate (ORR)

ORR is calculated as the proportion of subjects with a CR or PR. Subjects without at least one post-baseline response assessment will be treated as non-responders.

ORR and Pearson-Clopper 95% confidence interval (CI) will be displayed separately for CT-based response and FDG-PET (=PET-CT) based response. CR and PR rates and their Pearson-Clopper 95% CI will be also displayed separately.

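### Appendix A dates visits from SV while the protocol fixes scans to the calendar, so after a net visit shift of more than 7 days on-schedule scans can be labelled Unscheduled or placed one visit early

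*SAP*

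**What the plan says.** Protocol 5.4.9 sets imaging at screening and then "every 8 weeks for the first 3 assessments, then every 12 weeks thereafter". It adds: "This scheduling is regardless of any treatment/cycle delays that may occur". Scans are also required, in the words of Protocol 5.4.10, "as well as at the time of suspected clinical progression". Protocol 6.8 foresees delays: "AFM13 dosing delays may be permitted in the case of medical/surgical events or logistical reasons not related to study therapy". The visible text gives no maximum length.

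SAP 8.6.1.4 explains why a derivation is needed: "In the CRF, the post-baseline disease assessments are not linked to study visits". Appendix A supplies it. Step 1 takes the earliest and latest component dates of the assessment (`DateINF`, `DateSUP`). Step 2 gives the assessment a visit's name if either date lies within 7 days of `SV.SVSTDTC`, or if the two dates straddle that window. Otherwise `AVISIT` is Unscheduled. The notes say "Visits planned per protocol to have disease assessments are considered from SV", and one component inside the window carries the whole assessment with it.

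SAP 8.1 gives the consequence of the label: "Unless otherwise stated, unscheduled visit results will be included in date/time chronological order, within subject listings only". SAP 8.6.2 opens with "Within each visit an overall response will be determined by the IRC and Investigator", and its analysis table plans overall response, best overall response (BOR) and ORR for each cohort.

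**The concern.** The two documents run on different clocks. The scan follows the calendar. The window that names it follows the recorded visit date. When the visit date moves and the scan does not, a scan taken exactly when the protocol asks for it can fall outside every window, or fall inside the window of the wrong visit.

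The within-visit overall-response summaries are at stake. An Unscheduled scan is confined to listings, and a mislabelled one is counted at an earlier visit than it belongs to. The interim analysis lists overall response among its outputs, and Protocol 8.9 requires only one post-baseline assessment per subject at that point. One lost label could therefore remove a subject's only within-visit result there.

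**Working it through.** The plan states no figure on this point, so there is nothing to reproduce. The check applies Step 2 literally.

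**Inputs**
- Scan calendar (Protocol 5.4.9): Weeks 8, 16, 24, 36, 48, 60. With first dose as Day 1, planned day p = 7 × week + 1, giving Days 57, 113, 169, 253, 337, 421.
- Window (SAP Appendix A, Step 2): `SV.SVSTDTC` ± 7 days.
- Assumption: after a net delay of D days, the SV date of a planned visit is p + D, while the scan stays on day p. Counting from first dose is also an assumption, because the schedule is redacted.

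**Step 1: single-day scan on its planned day.** Scan j takes the name of visit i when |p_j − (p_i + D)| ≤ 7, that is, when p_j − p_i − 7 ≤ D ≤ p_j − p_i + 7.
- Own visit: p_j − p_i = 0, so D must be 0 to 7.
- One visit early, 8-week spacing: 113 − 57 = 169 − 113 = 56, so D from 49 to 63.
- One visit early, 12-week spacing: 253 − 169 = 84, so D from 77 to 91.

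| Delay before the first scan | Labels for the scans at Weeks 8, 16, 24, 36, 48, 60 |
|---|---|
| 0–7 days | all correct |
| 8–48 days | all Unscheduled |
| 49–63 days | Week 16 labelled Week 8; Week 24 labelled Week 16; the rest Unscheduled |
| 84 days | Weeks 36, 48, 60 labelled Weeks 24, 36, 48; the rest Unscheduled |

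**Step 2: later and repeated delays.** A delay of 8 to 42 days starting at Day 90 leaves Week 8 correct and makes Weeks 16 to 60 Unscheduled. Two 5-day delays, at Days 30 and 90, leave Week 8 correct (5 ≤ 7) and make the rest Unscheduled (5 + 5 = 10 > 7). The net shift is what counts.

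**Step 3: several component dates.** For delays up to 21 days, the scan keeps its own label when `DateSUP` reaches p + D − 7, that is, when scan lateness plus component spread is at least D − 7 days:
- D = 10: 3 days needed.
- D = 14: 7 days needed.
- D = 21: 14 days needed, for example a scan 7 days late with a 7-day spread.

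**Step 4: which endpoints use the label.**
- Overall response is determined within visits, so it is exposed to `AVISIT` and to the 8.1 default.
- BOR ranks all of a subject's assessments. The stated exclusions are responses after progression, new anti-cancer therapy or transplant. ORR is the proportion with CR or PR.
- DOR runs between dated events.

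None of these last three definitions refers to `AVISIT`.

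**Step 5: planned-day anchor.** If the window is centred on p, the distance for an on-schedule scan is |p − p| = 0 for any D. All six scans then map to their own visits.

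**The case against.** The strongest objection is that drift in SV dates is inferred. The SAP does not call these dosing visits or define `SV.SVSTDTC`, and the schedule is redacted. Protocol 6.8 gives some support for nominal-day scheduling. It allows ± 3 days per visit but also requires at least 3 days between doses. If each weekly visit were timed from the previous dose, the gap would never be below 7 − 3 = 4 days and that floor would be idle. It matters only if windows sit on nominal days, in which case a missed dose need not shift later visits. This stands as a limit on certainty. It does not remove the point, because Protocol 5.4.9 itself speaks of cycle delays and Appendix A takes the date from the subject's visit record.

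The multi-component rule also rescues some scans, as Step 3 shows. The Olsen assessment draws on many dated sources, so Cohort C may benefit more often.

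The SAP does not show the layout of a by-visit response table. Templates are in a separate document, and SAP Section 7 is not visible. Handling may be specified there.

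A reader might infer that the primary ORR is at risk, by applying the 8.1 default to BOR. The BOR definition is specific, covers all assessments and does not use the visit name, so the documents do not support that. For DOR, the missed-assessment thresholds do switch by cycle. However, they count days between assessments, and the SAP does not say that the cycle is read from `AVISIT`.

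**Conclusion.** The conflict between the two clocks is in the text. Given SV dates that move with the delay and scans on their planned days, a net shift of 8 to 48 days makes single-day scans after the delay Unscheduled. A shift of 49 to 63 days before the first scan puts the Week-16 and Week-24 scans one visit early. The affected scans leave the within-visit overall-response summaries or are misplaced in them.

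Two stronger readings do not hold. Not every scan of a delayed subject is lost: scans before the delay keep their label, and some later ones are rescued. Nor do the documents show that by-visit results become too favourable. Subjects with delays may be a selected group, but their CR and PR scans would drop out along with their progressions, and no by-visit denominator is stated. The documents give no frequency of delays, so the number of subjects affected is unknown. Labelling a symptom-driven scan Unscheduled is accurate in itself.

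This should be corrected, but it is a labelling defect with no shown effect on ORR, BOR or DOR.

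**What to change.** In Appendix A Step 2, replace `SV.SVSTDTC` with the planned assessment date counted from the first AFM13 dose: Day 57, 113, 169, then every 84 days. Keep the 7-day window. Planned dates are at least 56 days apart, so the 15-day windows do not overlap.

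In SAP 8.6.2, add that all disease assessments, scheduled or unscheduled, are used by date in BOR, ORR and DOR. This removes any doubt left by the 8.1 default and covers scans for suspected progression.

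Carrying an off-schedule progression into the next planned visit is not part of this change. It would be a new imputation, and Protocol 8.1.1 limits imputation of missing values to adverse-event and concomitant-medication dates.

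The cost is SAP wording and minor reprogramming with dates already collected. By-visit proportions may change slightly.
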